2.1. Trial Objectives

- Primary Objective

The key aim of this research in South Asian populations and White British populations, is to find out whether differences in COVID-19 morbidity and mortality in similar populations in the UK might be related to mucosal immunity expressed in the mouth and to the oral microbiome (the total bacteria, fungi and viruses living in the mouth). This will be achieved by determining

whether in the mouth there are differences between the participant groups of mucosal natural immunity (innate immunity), immune responses to SARS-COV2 antigens (adaptive immunity), or the oral microbiome

- Secondary Objectives

1. To determine whether differences in mucosal immunity or differences in the oral microbiome correlate with susceptibility to COVID-19 infection, or to progression and recovery from the disease.

2. To determine whether the presence of pre-existing oral disease is related to susceptibility to SARS-CoV2 infection, to severity of COVID-19 disease or relates to the nature of mucosal immunity and to the composition and activity of the oral microbiome

- Primary End Point

- Collection, processing and analysis of samples. Statistically significant quantitative differences in measured mucosal innate immune factors, mucosal adaptive immune factors and/or in the oral microbiome in relation to 1) a comparison between South Asian and White British populations in the UK 2) the degree of severity of COVID in South Asian and White British participants in the UK

- Secondary End point

- Generation of raw data.
- *a comparison between South Asian populations in the UK and in Chennai, India.

**Note: This is the UK part of an international research collaboration between the UK (funded by the MRC) and India (funded by the DBT) with research being carried out separately but in parallel in the two Countries and generating results which will be directly compared.*

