Each of the two population cohorts (South Asian and White British) has four sub-groups (clinically uninfected subjects, asymptomatic/mild, symptomatic moderate/severe, and recovered). After patient information sheets and consent, then oral health questionnaires (5mins), SWMF samples (5-15 mins), oral health (periodontal) examination (10 mins), and blood via venesection (5 mins). Patients will chew on a pellet of wax until approximately 4ml SWMF is recovered by drooling into sterile universal containers (between 5 and 10 minutes normally) after which the chewed wax will be wrapped in gauze and disposed with other clinical waste in adherence to infection control procedures. Blood samples may be taken before, during or after the SWMF collection. Repeat blood and stimulated SWMF will be taken at approximately 2 weeks, 4 weeks and 12 weeks after baseline for those participants willing to take part in the sequential studies. Oral examination and partial mouth recording will not be repeated unless any material change in oral condition is evident.

Uninfected subjects will be further defined as those who do not show antibodies to nuclear capsid protein antigens. The presence of such antibodies would indicate exposure to SARS-CoV2 rather than immunisation, and would be classified as asymptomatic if no history of symptoms.

Number of samples: With South Asian and White British participants, there will be up to 100 patient samples in each of the four sub-groups (uninfected subjects, asymptomatic/mild and moderate/severe disease, and recovered.). All will be assayed for immunological parameters, and the first 50 in each group for microbiome analysis, with the remainder stored for future analysis. The first 50 participants in each group will be invited to provide sequential samples.

Times of samples: There will be repeat samples of SWMF and blood at approximately 2, 4 and 12 weeks. Those SWMF at 4 weeks will be analysed for the microbiome in addition to the immunology (see table 1).

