Choice of time points: Mucosal immunological responses have a different and often shorter time frames than systemic responses. The 2 week post infection or post vaccination time point as well as the 4 week time point is to determine whether a response has been generated, and indicate possible kinetics of the mucosal response in comparison with systemic (serum) responses. The 12-week sampling point was selected as optimal to indicate longevity of any mucosal response, and any differential between a possible protective response of longer duration from a response of shorter duration.

Handling of samples: After collection, samples for GSTT haematology (Viapath) and blood glucose (if results not already available) will be sent to GSTT haematology. Study pseudoanonymised samples will be transported to the Centre for Host-Microbiome Interactions (CHMI) laboratories in Guy's Tower by the clinical research dentist. SWMF will be transported on ice. All samples will be subject to current infection control measures and containers pre-labelled. In the lab, SWMF samples will be centrifuged and immune factors including cytokines and anti-SARS-CoV2 antibodies assayed in the supernatant, whilst cellular factors determined in reconstituted pellet. DNA extraction for the microbiome studies will be performed on the saliva pellet. Peripheral blood T cell phenotypes will be assayed in the supernatant from plasma. Recruitment: Patients identified by the clinical team will be recruited by a clinical research assistant and consented. Uninfected subjects and ambulant patients will be recruited within Guys

and St Thomas' Hospital sites, from KCL sites and for General Medical Practice PIC (participant identification centre) sites. Symptomatic patients will be recruited from within outpatients or on the wards. From each subject, basic medical data will be collected and an oral health questionnaire applied, followed by SWMF, an oral examination and blood samples as above.

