3.1 Inclusion Criteria

Inclusion criteria
	
 • South Asian and White British persons and those diagnosed with symptomatic or asymptomatic COVID-19 infection, or recovered from COVID infection or previously uninfected. • Aged 18 or over. Able to understand and consent. • For inpatient groups: Confirmed COVID-19 positivity, symptoms and symptom onset within the past 21 days; Be recently (within 7 days) hospitalised with COVID-19 disease; Have COVID-19 disease proven by PCR testing for SARS-CoV-2 within the last 21 days; • Uninfected subjects: no history of COVID-19; not vaccinated; (negative for anti-SARS-CoV2 nucleoprotein antibodies at lab)
---------------------------	--

	
 • Recovered groups: Have had COVID-19 disease proven by PCR testing for SARS-CoV-2. • Those willing to participate on a single occasion but unwilling to participate with longitudinal samples will not be excluded. • Smoking, obesity, diabetes, heart disease, antibiotics or treatment related to COVID is not excluded.
--	--

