5.1 Central/Local Laboratories

Blood samples designated for routine blood tests and glucose will be sent to the hospital blood pathology lab for processing and analysis according to routine processes.

The remaining blood samples will be processed and prepared in the Centre for Host Microbiome laboratory on [name], Guy’s Hospital. Microbial DNA extraction will be performed in these laboratories. Extracted microbial DNA identified by study number only will be sequenced by specialised commercial companies or academic institutions in the UK or non UK.

The salivary microbiome will be analysed on 50-100 patients per group after microbial DNA extraction with standardised protocol, using shotgun metagenomic sequencing on an Illumina NovoSeq generating > 20 million reads/sample. Sequencing will be performed by a commercial provider. Analysis of the sequencing data will be performed at KCL under the supervision of CHMI academics as described in section 2.4. The salivary metabolome will be determined using NMR. The longitudinal immune response and shifts in the oral microbiota will be correlated with COVID-19 severity as well as both COVID-19 and non-COVID-19 oral disease. We will identify significant differences in oral microbiota & immune responses during transition from viral to immunological to post-COVID-19 phases, identifying specific host factors as therapeutic targets.

Salivary secretory IgA antibody assay to study mucosal responses to antigens associated with COVID-19.

SARS is a closely related virus to SARS-CoV2. Several crystal structures have been published that describe how different antigens recognize the SARS spike protein receptor binding domain. These highlighted antigenic regions in the SARS spike protein. Structures are also now available for the homologous SARS-CoV2 spike protein receptor binding domain. The amino acid sequence of the spike protein from SARS & SARS-CoV2 were compared. Major differences were identified and 10 peptides constructed. Three of these have been selected and will be assayed by ELISA along with Capsid antigens obtained commercially. The group has extensive experience with ELISA techniques, and has performed preliminary experiments to verify their use in SWMF. (This kit has been developed and validated in King's College London, and methodology shared with VHS, Chennai for sample testing.)

Blood and SWMF lymphocyte phenotyping

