5.5 Data Recording/Reporting

The data obtained during this study will comply with community standards for research data. King's College London aspires to ISO 27001 standards for data security. All hard copy data and link codes will be kept in a GSTT locked and secure filing cabinet in a locked room based in the PI's office Department of Periodontology, Faculty of Dentistry, Oral and Craniofacial Sciences in Guys Dental Hospital. Additional back up of link codes will be stored on secure GSTT storage. All pseudoanonymised electronic data will be held on KCL firewalled computers, subject to KCL standard audits. In addition, data will be stored at KCL high performance computers with weekly backup program. Data will be recorded by a dedicated technician who will be HTA trained.

Data analyses:

The immunological markers will be compared between the healthy controls, asymptomatic and symptomatic COVID-19 patients using Mean, Median and non-parametric tests like Anova and Mann-Whitney rank sum tests. The immunological markers in the blood and SWMF will be compared and analysed at various time points of the disease progression. The key immunological parameters will be compared with the oral microbiome data to identify key biomarkers that may be indicative of the pathogenesis of the disease. These parameters will also be compared between the South Asian and the British-Caucasian population recruited in the UK. At the conclusion of the study, all the above analyses of the immunological and oral microbiome parameters will be compared among the age-matched and disease-matched participants in the UK and a collaborative, parallel study performed by collaborators in Chennai, India.

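### Capsid antibody both defines the uninfected groups and is compared with them as a read-out, so uninfected-versus-infected contrasts on it are inflated by the selection rule

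*Protocol*

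**What the plan says.** **Group definition.** Protocol section 2.2 states: "Uninfected subjects will be further defined as those who do not show antibodies to nuclear capsid protein antigens". Section 3 repeats the rule, and section 3.1 lists among the conditions for uninfected subjects "negative for anti-SARS-CoV2 nucleoprotein antibodies at lab". A person recruited as uninfected who proves antibody-positive "would be classified as asymptomatic if no history of symptoms" (section 2.2).

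**Read-out.** Section 5.1, under the salivary secretory IgA assay, describes ten constructed spike peptides and continues: "Three of these have been selected and will be assayed by ELISA along with Capsid antigens obtained commercially". Section 2.2 has "immune factors including cytokines and anti-SARS-CoV2 antibodies assayed in the supernatant" of the mouth fluid (SWMF). The synopsis lists both serum and secretory antibodies to viral antigens among the measurements.

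**Comparison.** Section 5.5 states: "The immunological markers will be compared between the healthy controls, asymptomatic and symptomatic COVID-19 patients". No marker is excepted. The primary end point (section 2.1) covers innate factors, adaptive factors and the microbiome in relation to "a comparison between South Asian and White British populations in the UK" and "the degree of severity of COVID in South Asian and White British participants in the UK".

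**How infected participants enter.** By sections 3 and 3.1 they enter mainly on a viral test: carriage on routine testing or a positive antigen test for asymptomatic/mild, RT-PCR for moderate/severe, and past PCR-proven disease for recovered.

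The protocol does not state the fluid, isotype or cut-off of the test that defines the uninfected groups.

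**The concern.** One marker does two jobs. It decides who may be in the uninfected groups, and it is then tested between those groups and the infected ones. Cutting off the upper part of the control distribution lowers the control values before any comparison is made. Moving symptom-free positives into the asymptomatic category raises the other side as well. A low p-value would then reflect the selection rule to an unknown degree.

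Adaptive response to viral antigens is part of the primary objective, and the introduction promises diagnostic and prognostic utility from comparing patients with controls. A marker that defines the controls will look diagnostic against them: if the defining assay is used as the diagnostic test at its own cut-off, its specificity is 100% by construction.

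**Working it through.** The protocol gives no figure on this point to reproduce: no alpha, effect size, standard deviation or antibody prevalence. What follows is an illustration on stated assumptions.

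**Inputs from the protocol.** Up to 100 per sub-group (section 2.2) and a minimum of 50 cross-sectionally (table 1 notes, section 2.4). Mann-Whitney is the two-group test (sections 2.4 and 5.5).

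**Assumptions.**
- Two-sided 5% test.
- Antibody level standard normal in both source populations, so no true difference.
- *p*: share of clinically uninfected recruits above the cut-off, 10% to 70%.
- *rho*: correlation between the defining assay and the read-out.
- *q*: share of the asymptomatic group made up of reclassified positives, 0 or 20%.

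**Step 1: built-in shift.** With cut-off c at the (1 - p) quantile and phi the normal density, the retained controls have mean -rho x phi(c)/(1 - p) and the reclassified positives have mean rho x phi(c)/p. The built-in difference in SD units is

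rho x [phi(c)/(1 - p) + q x phi(c)/p].

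- p = 0.3, rho = 1, q = 0: 0.348/0.7 = 0.50 SD.
- p = 0.3, rho = 0.5, q = 0: 0.25 SD.
- p = 0.1, rho = 1, q = 0.2: 0.1755/0.9 + 0.2 x 0.1755/0.1 = 0.195 + 0.351 = 0.55 SD.
- rho = 0: zero.

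**Step 2: rejection rate with no true difference** (simulation, 1,500 runs per setting):

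| n per group | p | rho=1, q=0 | rho=0.5, q=0 | rho=0, q=0 | rho=1, q=0.2 | rho=0.5, q=0.2 |
|---|---|---|---|---|---|---|
| 50 | 10% | 13% | 7% | 5% | 69% | 23% |
| 50 | 30% | 76% | 24% | 5% | 98% | 45% |
| 50 | 50% | 99% | 51% | 6% | 100% | 66% |
| 50 | 70% | 100% | 84% | 5% | 100% | 90% |
| 100 | 10% | 24% | 10% | 5% | 96% | 44% |
| 100 | 30% | 96% | 41% | 5% | 100% | 73% |
| 100 | 50% | 100% | 82% | 5% | 100% | 93% |
| 100 | 70% | 100% | 98% | 5% | 100% | 99% |

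Reclassification matters most when few recruits are positive: at p = 10% and n = 100 it takes the rate from 24% to 96%.

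**Step 3: diagnostic accuracy with no true difference, rho = 1.** An infected value lies above the cut-off with probability p and then exceeds every control; otherwise it exceeds a control half the time. So AUC = p + (1 - p)/2 = 0.5 + p/2, which is 0.55, 0.65 and 0.75 at p = 10%, 30% and 50%. With q = 0.2 and p = 10% it is 0.8 x 0.55 + 0.2 = 0.64.

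**Step 4: positive/negative read-out.** If the defining assay is the read-out, the uninfected groups are 0/n. With six positives in the other group, two-sided Fisher p = 2 x C(n,6)/C(2n,6): 0.024, 0.027 and 0.029 at n = 30, 50 and 100. Five positives do not suffice (0.052, 0.056, 0.059). If 20% of the other group is positive, six or more occur with probability 0.95 at n = 50 and about 1.00 at n = 100. SA1 against WB1 is 0/n against 0/n.

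**The case against.** **Infected participants are not selected on this marker.** This stands. They enter mainly by PCR or antigen test, so their capsid antibody is real data and a real difference is likely. A reader might infer that every capsid-antibody difference is manufactured by the group definition. The documents do not support that: the difference is inflated, and the built-in part cannot be separated from the real part.

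**A null with equal distributions is unrealistic.** Also fair. If infected participants were 1 SD higher (an assumption), an untruncated comparison would already reject in over 99% of runs at 50 or 100 per group, so selection would hardly change the test decision. It would still change the estimate: with rho = 1, p = 30% and q = 0, the mean difference becomes 1.00 + 0.50 = 1.50 SD.

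**The defining test may not be the read-out.** Section 5.1 names capsid only under salivary secretory IgA, and the defining test could be serological. This limits the size, and a salivary comparison of two seronegative ethnic groups could be legitimate, so SA1 against WB1 is uninformative only for the defining assay. It does not remove the problem. The synopsis lists serum and secretory antibodies as measurements, and any positive correlation between the fluids carries some of the selection over.

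**Reach.** A reader might infer that a whole primary domain is compromised. It is not. Spike-peptide antibodies, cytokines, cell phenotypes and the microbiome define no group, and capsid contrasts among participants who entered by viral test are sound.

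**An analysis plan could settle this.** Section 5.5 is generic, and a plan not shown may be more specific. But the protocol itself fixes both the group rule and an unrestricted comparison; followed as written, the result is biased. Using capsid antibody to separate infection from immunisation is reasonable and is not the defect.

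**Conclusion.** The point holds for one marker and one kind of contrast. A comparison of capsid antibody between uninfected and infected groups, above all against the asymptomatic category that receives the reclassified positives, is inflated by the group definition. On the control side it is fully circular if the defining assay is the read-out, partly so if the two are correlated, and not at all if they are unrelated. With no true difference, 100 per group, 30% of recruits above the cut-off and no reclassified positives, the corresponding rejection rates are 96%, 41% (correlation 0.5) and about 5%. The share positive, the correlation and the reclassified share are assumptions, because the protocol gives none of them.

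The p-value, effect size and diagnostic accuracy from such a contrast should not be reported as biological findings. This warrants a wording change; it does not undermine the study's other comparisons.

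**What to change.** In section 5.5:

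1. Name the assay that defines the uninfected groups, with its fluid, isotype and cut-off, and declare it a classification variable.
2. Exclude that assay from inferential, correlation, regression and diagnostic-accuracy analyses that include SA1 or WB1.
3. Report capsid antibody in the other fluid descriptively for those contrasts, with the selection stated.
4. Keep capsid antibody as an outcome only among participants who entered by PCR or antigen test (severity contrasts, and South Asian against White British within those groups), leaving out anyone reclassified on capsid antibody. This requires flagging reclassified participants in the data.

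The cost is wording and one flag, with no extra samples or visits. One read-out is lost from inference in contrasts with the uninfected groups. Reporting the other fluid descriptively keeps salivary data that a ban covering both fluids would discard.

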The gene richness analysis will be done based on the updated count matrix to obtain the diversity of the samples at the gene level. A Wilcoxon test follow by Benjamini-Hochberg multiple testing correction will be used to obtain the significant changes between the cohorts. Next, we will map each sample to our already generated 1,942 oral Metagenomic Species Pangenomes (MSP), as an updated format for the metagenome species. The relative abundance of an MSP will be calculated using the mean abundance of its 100 ‘marker’ genes. To contrast the species abundance in different cohorts, we will perform Benjamini-Hochberg multiple testing correction of a Wilcoxon test. Functional analysis will also be performed using the PFAM and KEGG databases. Antimicrobial resistance analysis will be performed by searching reads using the CARD (Comprehensive Antimicrobial Resistance Database) database. In addition, “ortotyping” will be performed using the microbial information on the genus-level abundance with a Hellinger transformation with a Dirichlet multinomial mixtures (DMM) approach to cluster individual samples to distinct groups based on their microbiome composition, and a Fisher’s exact test will be used to identify the prevalent ortotype.

3. Sample Size, Selection and Withdrawal of Subjects

The success of the national vaccination programme has necessitated casting the recruitment net more widely than originally anticipated. Sample size is discussed in 2.4

Uninfected (vaccinated or unvaccinated) will be identified by advertising within KCL and GSTT sites, and at PIC sites, via social media and by recruitment at vaccination centres at GSTT or

testing centres at KCL/GSTT. Patients admitted to wards for non-COVID reasons and found to be SARS-CoV2 negative will be invited to participate. Uninfected (vaccinated) will be identified by recruitment at vaccination centres and by advertising within KCL and GSTT and PIC sites. Uninfected participants will be further defined as those who do not show antibodies to nuclear capsid protein antigens. The presence of such antibodies would indicate exposure to SARS-CoV2 rather than immunisation, and would be classified as asymptomatic if no history of symptoms.

All will be given the Patient Information Leaflet (PIL) about the study and access to the study website (<https://www.kcl.ac.uk/research/mimsa>)

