Asymptomatic/mild subjects will be recruited from those identified as positive for SARS-CoV2 carriage in routine testing at KCL or GSTT. In both cases local staff will inform them about the trial and give out a patient information sheet. A medical history will be taken from those who consent to take part in the research

Symptomatic moderate/severe patients will be recruited within Guys and St Thomas Hospital, mainly in conjunction with the GSTT COVID infection teams. Patients will be recruited from those admitted or planned to be admitted to GSTT with a recent onset (≤ 21 days) of symptoms of COVID-19 and a confirmed positive nasal/nasopharyngeal PCR test for SARS-CoV-2. They will be identified and approached by the clinical staff caring for them on the wards who will discuss the trial in outline and offer the PIL. Should the patient wish to consider participation after reading the PIL, the clinical research dentist (summoned by clinical ward staff) will obtain signatures of consent.

Recovered participants will be patients who have had COVID and fulfil the inclusion criteria. They will have either been discharged from GSTT or be attending either the post-COVID or ICU follow-up outpatient clinics and will be sent letters of invitation to participate. They will also be recruited from participating GP PIC sites, KCL sites and GSTT sites

Number of subjects	Subject selection
Group 1. SA1, BW1 Uninfected Subjects (n=100 each)	Uninfected subjects, both South Asian and White British will be recruited by advertisement within KCL or social media, from non-COVID in-patients or outpatients or attending A&E at GSTT and at SARS-CoV2 antigen testing centres and vaccination centres and at PIC sites. They will be furnished with the participant information leaflet and invited to take part in the study. After obtaining informed consent, oral examination, oral & general health questionnaires and samples of blood and stimulated whole mouth fluid (SWMF) (see below) will be taken either on the wards (inpatients), A&E or at the department of Oral Medicine at Guys Hospital
Group SA1v, BW1v (n=50)	In a subset of uninfected subjects from those attending for vaccination or volunteers, blood and SWMF will be taken 2 weeks after the first vaccination and 2 weeks after the second vaccination for immunology and microbiome analysis.

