
Group 2. SA2, BW2. Asymptomatic/mild n=100 each
	
Asymptomatic/mild SARS-CoV2 positive group Volunteers or subjects attending SARS-CoV2 testing centres who are found to be antigen positive or In-patients who have positive Covid tests and designated as asymptomatic/mild but admitted for non-covid reasons or those attending A&E with COVID but designated as mild/asymptomatic will be furnished with the participant information leaflet and invited to take part in the study After obtaining informed consent, oral examination, oral health & medical history questionnaires and blood and stimulated whole mouth fluid (SWMF) (see below) will be taken at the department of Oral Medicine at Guys Hospital or on the wards or in A&E at GSTT and KCH. Groups of 100 South Asian and White British participants will be recruited.

Groups 3 SA3, BW3 n=100 each
	
Moderate/Severe Symptomatic patients Patients either seen at GSTT or admitted as in-patients to GSTT or KCH and found to be SARS-CoV2 positive by RT-PCR in nasopharyngeal samples and designated as moderate/severe on the NIH/NIMR COVID severity scale will be furnished with the participant information leaflet and invited to take part in the study and will be enrolled in the study after obtaining written informed consent. After obtaining informed consent, oral examination, oral health & medical history questionnaires and blood and stimulated whole mouth fluid (SWMF) (see below) will be taken at the department of Oral Medicine at Guys Hospital or on the wards or in A&E. Groups of 100 South Asian and White British participants will be recruited.

Groups 4. SA4, BW4 n=100 each
	
'Recovered' patients These will be patients who have had COVID. They may be invited directly to participate by advertising at sites specified above or be attending either the post-COVID or ICU follow-up outpatient clinics. Patients may cover the COVID severity range and include those with a severe/moderate COVID history. Those attending the post-COVID clinic may include those referred in by primary care including those with long-COVID. Covid positive patients discharged from GSTT and fulfilling the inclusion criteria will be sent letters of invitation to participate. This data is available to the COVID clinical research team and participants will be identified with the Clinical Research Dentist.

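### Volunteers with capsid antibody and no symptoms are classed as asymptomatic without a viral test or infection date, which conflicts with recruiting the asymptomatic/mild group on a current positive test

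*Protocol*

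**What the plan says.** Section 2.2 divides each population into "four sub-groups (clinically uninfected subjects, asymptomatic/mild, symptomatic moderate/severe, and recovered"). Someone recruited as uninfected is checked later in the laboratory. Section 3 states: "Uninfected participants will be further defined as those who do not show antibodies to nuclear capsid protein antigens". Sections 2.2 and 3 both then say what happens to those who do show them: "The presence of such antibodies would indicate exposure to SARS-CoV2 rather than immunisation, and would be classified as asymptomatic if no history of symptoms". Neither place sets a time window or asks for a viral test.

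Section 3 recruits the asymptomatic/mild group differently: "Asymptomatic/mild subjects will be recruited from those identified as positive for SARS-CoV2 carriage in routine testing at KCL or GSTT". Its group table, under a heading for a SARS-CoV2 positive group, lists "Volunteers or subjects attending SARS-CoV2 testing centres who are found to be antigen positive", in-patients with positive tests admitted for other reasons, and A&E attenders with mild or asymptomatic COVID.

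Section 3.1 sets this condition for the recovered groups: "Have had COVID-19 disease proven by PCR testing for SARS-CoV-2". The only recency limit there is restricted: "For inpatient groups: Confirmed COVID-19 positivity, symptoms and symptom onset within the past 21 days".

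**The concern.** Capsid antibody shows infection at some time, possibly many months before sampling. The protocol itself treats it as evidence of exposure. A positive antigen or carriage test concerns infection now. If both routes lead into SA2/WB2, that group has no single biological meaning, and nothing in the protocol requires the two kinds of member to be told apart.

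The primary end point in section 2.1 has two parts: South Asian versus White British, and degree of COVID severity. Section 5.5 compares immunological markers between healthy controls, asymptomatic and symptomatic patients. Group 2 enters all of these.

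Timing suffers too. Section 2.2 justifies the 2- and 4-week samples as showing whether a response has been generated after infection or vaccination. For an antibody-only member, a visit counted from baseline has no known relation to infection.

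**Working it through.** **1. Which group can take these volunteers?** The person considered was recruited as uninfected, is capsid-antibody positive, reports no symptoms and has no PCR-proven past disease.

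| Group | Entry rule | Open to this person? |
|---|---|---|
| 1 Uninfected | No capsid antibody (2.2, 3, 3.1) | No |
| 2 Asymptomatic/mild | Current positive test (section 3) | By label yes, by recruitment rule no |
| 3 Moderate/severe | RT-PCR positive and graded moderate/severe (section 3) | No |
| 4 Recovered | Past disease proven by PCR (3.1) | No |

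Only Group 2 carries the label that the rule assigns, and its recruitment text does not cover the person.

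**2. Visit schedule.** Table 1 gives Group 2 a sample at 10–14 days and the uninfected group none. Section 2.2 says samples are batch analysed, so the antibody result may arrive after that visit was due.

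**3. The plan's own figure.** Section 2.4 gives 30 to 50 values per parameter, without alpha, power, effect size or SD, so it cannot be reproduced. The point does not depend on it. Assuming two-sided 0.05 and 80% power, 50 per group corresponds to d = (1.96 + 0.84) × √(2/50) = 0.56 SD.

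**4. Group 2 versus uninfected (illustration).** Let f be the share of Group 2 that is antibody-only, assumed to resemble uninfected people on an acute marker. The mean shift becomes d(1 − f). By normal approximation, power = Φ(d(1 − f)√(n/2) − 1.96). With n = 50, √(n/2) = 5.

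| f | Shift, d = 0.8 | Power, formula | Power, Mann–Whitney simulation (4,000 runs) | Power, formula, d = 0.56 |
|---|---|---|---|---|
| 0% | 0.80 | Φ(2.04) = 98% | 97% | Φ(0.84) = 80% |
| 20% | 0.64 | Φ(1.24) = 89% | 86% | Φ(0.28) = 61% |
| 40% | 0.48 | Φ(0.44) = 67% | 60% | Φ(−0.28) = 39% |

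At the maximum of 100 per group, d = 0.8 and f = 40% still give Φ(0.48 × √50 − 1.96) = Φ(1.43) = 92%. The estimate is still shrunk to 0.48 SD.

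**5. Group 2 versus moderate/severe.** If the true difference is δ in an acute marker that rises with severity, lowering Group 2's mean by 0.8f turns it into δ + 0.8f. That is 0.16 SD wider at f = 20% and 0.32 SD wider at f = 40%. Antibody end points may move in another direction, since past infection can raise them.

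**6. South Asian versus White British within Group 2.** With no true ethnic difference, f = 40% in one population and 10% in the other gives a spurious shift of (0.40 − 0.10) × 0.8 = 0.24 SD. In simulation the Mann–Whitney test then rejects in about 18% of runs at 50 per group and 34% at 100, instead of 5%.

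**7. Could f be that large?** Finding 50 seronegatives at seroprevalence p yields 50p/(1 − p) seropositives. Assume 25–50% of them report no symptoms and Group 2 closes at 50.
- p = 30%: 21.4 seropositives, 5 to 11 reclassified, f = 11–21%.
- p = 50%: 50 seropositives, 12.5 to 25 reclassified, f = 25–50%.

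Both inputs are assumptions. The protocol gives neither.

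**The case against.** The rule does not name SA2/WB2. *Asymptomatic* is also a severity label: section 2.2 speaks of people who have, or have had, asymptomatic to severe disease, the synopsis admits current or past infection, and section 3 lets recovered participants span the severity range. This stands to the extent that placement in Group 2 is an inference. It does not remove the conflict. Those passages govern entry to the study or describe a group that 3.1 closes to people without PCR proof. If Group 2 was not meant, these volunteers have no group.

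Several stronger readings are tempting, and the documents do not support them.
- **That the reclassified volunteers are known to be virus-negative.** Section 3 mentions a negative test only for ward patients admitted for other reasons. For advertised volunteers no viral test is stated either way.
- **That the primary end point is a gradient from uninfected to severe.** Section 2.1 names degree of severity. The comparison with controls comes from section 5.5.
- **That every severity comparison loses power.** The loss applies to Group 2 versus uninfected. Against moderate/severe patients the difference would tend to widen.
- **That a seropositive person with past symptoms but no PCR proof is wrongly left out.** Such people may simply be ineligible, although the protocol does not say so.

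It is also fair that the uninfected criteria ask for no history of COVID-19, so population seroprevalence may not carry over. That screen could equally raise the share without symptoms.

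**Conclusion.** The point holds as a conflict between the classification rule in sections 2.2 and 3 and the entry criteria in sections 3 and 3.1. Applied as written, with Group 2 as the only matching label, the rule mixes current infections with past infections of unknown date. It biases comparisons of Group 2 with both its neighbours, in different directions, and can produce an ethnic difference if the mix differs between populations. It also leaves the follow-up samples of these members without a known time since infection.

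This is a faulty rule, not detail left for an analysis plan, because it decides group membership. The power figures are illustrations. They rest on an assumed 0.8 SD (or 0.56 SD) shift, an assumed antibody-only share, and the assumption that such members resemble uninfected people on acute markers. The true share cannot be derived from the protocol, and the conflict does not depend on it.

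**What to change.** Reconcile the rule in 2.2 and 3 with the criteria in 3 and 3.1:
- State that SA2/WB2 requires a positive antigen or PCR test at baseline.
- Flag capsid-positive participants who have neither such a test nor PCR-proven past disease as a separate category, past infection of unknown date. Keep it outside the group comparisons and the per-group counts, and report it descriptively or in a sensitivity analysis.

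Excluding these volunteers outright would also resolve the conflict, but would give up samples already taken.

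The cost is that Group 2 fills more slowly. The section 3 group table, Table 1 and section 3.1 need matching edits, so the change goes beyond the two sentences that carry the rule. It should be made before group membership is fixed for analysis.
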